Participants will receive technetium-99m sulfur colloid (Tc-99mSC) or Lymphoseek as part of SoC for SLN biopsy. In case the participant needs other surgery (e.g., lumpectomy, mastectomy etc.) on the same day of study drug administration, the other surgery is allowed once the SLN biopsy has completed. In the operating room, participants will receive ASP5354. After administration of ASP5354, visualization of the LN(s) will be assessed using a near-infrared fluorescence (NIR-F) imaging system followed by confirmation with the gamma probe. Once lymphatic mapping is completed, gamma probe will be used per SoC. For all the LNs observed by ASP5354, gamma probe will be attempted to measure radioactivity. If the LN is not observed with NIR-F after approximately 15 minutes following injection for breast cancer participants and approximately 15 to 30 minutes for melanoma participants depending on the location of the tumor and LNs, the investigator can proceed to use the gamma probe for LN detection. When the LN is detected with the gamma probe first, radioactivity will be measured and then NIR-F imaging should be attempted again for LN visualization. For participants with melanoma, usage of lymphoscintigraphy or single photon emission computed tomography (SPECT) as part of SoC is also allowed.

The visualization data to be collected will be consist of following:

- The visualization of the LN(s) will be assessed by the investigator intraoperatively using a binary “Yes or No” question.
 - If “Yes,” the time of surgical identification of LN(s) will be collected by the investigator.
 - If “Yes,” the number of LNs visualized and the number of LNs visualized with histopathology confirmed LN will be also assessed by the investigator.

Note: Histopathology review will be conducted per standard practice at each site.

- Transdermal visualization of lymphatic spread of ASP5354 after injection of the drug will also be assessed using a binary “Yes or No” question.
- The fluorescence intensity of the LN will be qualitatively assessed using a Likert Scale (0 = None; 1 = Mild; 2 = Moderate; and 3 = Strong).
- The radioactivity count will be collected for all the LNs identified by ASP5354 and/or SoC.
- The number of LN(s) with metastatic spread will be assessed by the investigator based on histopathologic review.

Note: Histopathology review will be conducted per standard practice at each site.

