4 STUDY DESIGN AND DOSE RATIONALE

4.1 Overall Study Design

The study is an open-label, dose-finding study to determine the optimal dose for LN visualization, as part of lymphatic mapping, in adult participants with breast cancer and melanoma undergoing SLN biopsy as part of Standard of Care (SoC).

Enrollment of breast cancer and melanoma participants will be performed independently and simultaneously. Dose level 2 (0.2 mg) will enroll the first 3 participants in each indication and then the Visualization Review Committee (VRC) will review the data for the breast cancer group and the melanoma group separately. If LN visualization with histopathologic confirmation occurs in the first 3 participants in each indication, then dose level expansion will occur and an additional 3 participants in each indication will be enrolled first with the 0.05 mg dose, followed by another 3 participants with the 0.6 mg dose. An interim analysis will be performed across initial dose levels (0.05, 0.2 and 0.6 mg) separately for breast cancer and melanoma by the VRC prior to further enrollment of participants.

If < 3 participants at 0.2 mg dose level have LN visualization with histopathologic confirmation on VRC review, 3 participants will be enrolled sequentially in the 0.6 mg and 1 mg dose levels. An interim analysis will then be performed across initial dose levels (0.2, 0.6 and 1 mg) separately for breast cancer and melanoma by the VRC prior to further enrollment of participants.

Dose Arm/IP Name	ASP5354 Dose Level	ASP5354 Dose Conc and Volume	Number of Participants
Breast Cancer and Melanoma 0.05 mg/ASP5354	0.05 mg	1.0 mg/mL, 0.05 mL in total	Up to 12
Breast Cancer and Melanoma 0.2 mg/ASP5354	0.2 mg	1.0 mg/mL, 0.2mL in total	Up to 12
Breast Cancer and Melanoma 0.6 mg/ASP5354	0.6 mg	1.0 mg/mL, 0.6 mL in total	Up to 12
Breast Cancer and Melanoma 1 mg/ASP5354	1 mg	1.0 mg/mL, 1 mL in total	Up to 12
Breast Cancer and Melanoma 2 mg/ASP5354	2 mg	1.0 mg/mL, 2 mL in total	Up to 12
Breast Cancer 4 mg/ASP5354	4 mg*	1.0 mg/mL, 4 mL in total	Up to 12

Conc: concentration

* The 4 mg dose level will be added only for breast cancer participants.

Depending on the outcome of the interim VRC analysis, additional participants may be added to the same dose level, a dose level may be closed, or a new dose level (1 mg, 2 mg or 4 mg [breast cancer only]) will begin enrollment. Up to 12 participants will be assigned at each dose level for both breast cancer and melanoma.

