7.1.1 Primary and Secondary Efficacy Assessments

Either during or post-operatively, the investigator will evaluate the details of all the LNs identified either by ASP5354 or Gamma Probe. These data will be captured to eCRF.

Following data is captured in eCRF per participant.

- Identification of at least 1 LN detected by ASP5354 and/or Tc-99mSC or Lymphoseek
- Times of injection of ASP5354 and Tc-99mSC or Lymphoseek
- Location (i.e., 3 and 9 o'clock) of ASP5354 administration
- Time of start of surgery
- Time of surgical identification of the LN(s) by ASP5354
- Time of incision for lymphatic mapping
- Time of removal of first LN
- Time of end of surgery
- Transdermal visualization of lymphatic spread of ASP5354 after injection

Following data is captured in eCRF per LN.

- “Sentinel LN” or “Non-sentinel LN”
- Method of identification (ASP5354 and/or Tc-99mSC or Lymphoseek)
- Dissection of LN tissue identified*
- Histopathologic confirmation of LN tissue by pathologist*

- Histopathologic confirmation of metastatic spread by pathologist*
- Likert scale:
The intensity of fluorescence will be qualitatively assessed during surgery by the investigator, by direct examination of the LN. Likert Scale (0 = None, 1 = Mild, 2 = Moderate and 3 = Strong) will be used to determine the intensity of fluorescence at the time point of the LN identification.
- Radioactivity count:
The radioactivity count of all the LNs identified by ASP5354 and /or Tc-99mSC or Lymphoseek will be counted with gamma probe.
* may not be collected in case of Non-Sentinel LN

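### Protocol 7.1.1 lets the ASP5354 identification entries be completed post-operatively, whereas 1.1, 4.1 and Table 1 make the visualization call intraoperative, and the SAP does not say which entry counts

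*Protocol*

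**What the plan says.** Protocol 1.1 (Study Design Overview) and 4.1 carry the same sentence: "The visualization of the LN(s) will be assessed by the investigator intraoperatively using a binary" Yes-or-No question. Table 1 marks the investigator's evaluation of LN visualization once, in the intraoperative column. Footnote 15 to that table places both the incidence of visualization and the Likert intensity score within this evaluation.

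Protocol 7.1.1, which sets out what goes into the eCRF, opens differently: "Either during or post-operatively, the investigator will evaluate the details of all the LNs identified either by ASP5354 or Gamma Probe". Two lists follow. The per-participant list starts with "Identification of at least 1 LN detected by ASP5354 and/or Tc-99mSC or Lymphoseek". The per-node list includes "Method of identification (ASP5354 and/or Tc-99mSC or Lymphoseek") and "Histopathologic confirmation of LN tissue by pathologist". None of these three items has a timing of its own. The Likert score does: "The intensity of fluorescence will be qualitatively assessed during surgery by the investigator, by direct examination of the LN", and the scale "will be used to determine the intensity of fluorescence at the time point of the LN identification". The per-participant list also collects the time of surgical identification by ASP5354.

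These entries are used in three places:

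- **First VRC review (Protocol 4.1).** If all of the first 3 participants at 0.2 mg have confirmed visualization, 0.05 mg and 0.6 mg follow. The other branch, to 0.6 mg and 1 mg, applies under this condition: "If < 3 participants at 0.2 mg dose level have LN visualization with histopathologic confirmation on VRC review".
- **Optimal dose (SAP 4.3.1).** Whether LN tissue was visualized is one of the listed VRC inputs.
- **Secondary endpoints (SAP 4.4.1.1 and 4.4.1.2).** Nodes, and participants with at least one node, are counted as identified by ASP5354 with histopathologic confirmation. Nothing says when that attribution must have been made.

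**The concern.** The protocol gives two timings for the same observation, and the looser one sits in the section that governs data capture. A site that entered the ASP5354 attribution after the pathology report had come back would be complying with 7.1.1, and the SAP would count the entry. The study is open-label, treating investigators sit on the VRC (Protocol 10.1.5.1), and external image reading is described only for the signal background ratio. No independent Yes/No read, and no lock of the call before pathology, is described.

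At stake are the branch taken after the first 3 participants, the visualization data on which doses are compared, and the ASP5354 detection proportions, including the comparison with the technetium agents. A node found by gamma probe and later credited to ASP5354 would favor ASP5354 only, and there is more room for this at doses with more misses.

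**Working it through.** The plan states no figure on this point, so there is none to reproduce. The check is mainly a comparison of texts, followed by an illustration of sensitivity.

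**1. Timing by item**

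| Item | 1.1, 4.1, Table 1 | 7.1.1 |
|---|---|---|
| ASP5354 visualization, Yes/No | Intraoperative | Participant-level identification item: during or after surgery |
| Agent that identified each node | Not separately timed | During or after surgery |
| Likert score | Intraoperative (footnote 15) | During surgery, at identification |
| Histopathology | Not timed | During or after surgery |

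Section 7.1.1 fixes the timing of Likert explicitly but makes no such exception for the two identification items.

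**2. Does the SAP close the gap?** Footnotes c and d in SAP 4.4.1.1 define the denominator as nodes identified intraoperatively and confirmed by histopathology. That says when the node was found, not when it was attributed to ASP5354. Let D be that denominator, A the confirmed nodes credited to ASP5354 and S those credited to standard of care. The reported proportions are A/D and S/D. If a confirmed node first credited to standard of care alone is later credited to ASP5354 as well, they become (A+1)/D and S/D, and the difference rises by 1/D. Only the ASP5354 side moves.

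**3. Weight of one participant-level call.** In a group of 3 it is 1/3 = 33.3 percentage points; in a full group of 12 it is 1/12 = 8.3 points. By the exact method named in SAP 4.1, the 95% interval is 9.4% to 99.2% for 2/3 and 29.2% to 100% for 3/3. The intervals overlap heavily, yet the two results lead to different next doses.

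**4. Illustration for the 3-of-3 rule.** Inputs: n = 3 and the 3-of-3 condition, from Protocol 4.1. Assumptions that are not in the documents: p, the true intraoperative rate of confirmed visualization, and m, the chance that a true miss is later entered as a success. The apparent rate is q = p + (1 − p)m, and P(3/3) = q³.

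| p | m = 0 | m = 0.10 | m = 0.25 |
|---|---|---|---|
| 0.6 | 0.600³ = 0.216 | 0.640³ = 0.262 | 0.700³ = 0.343 |
| 0.8 | 0.800³ = 0.512 | 0.820³ = 0.551 | 0.850³ = 0.614 |
| 0.9 | 0.900³ = 0.729 | 0.910³ = 0.754 | 0.925³ = 0.791 |

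The table shows how sensitive a 3-of-3 rule is to a single changed call. It does not estimate what 7.1.1 would do.

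**The case against.** The best reply is that the texts can be read together. Section 7.1.1 speaks of details of nodes already identified, and its lists mix operating-room times and gamma counts with pathology results that normally come later. A during-or-after wording is needed to complete such a record and need not mean that the call may be made again. Table 1 is specific, Section 7 of the protocol makes adherence to it essential, and 10.1.8 requires contemporaneous source data. This reading is fair, and probably what was intended. But the list includes the identification call itself without exception, so a late entry would not breach 7.1.1.

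Second, there are safeguards. Likert is scored per node during surgery with 0 meaning none, so a later Yes would clash with a recorded 0. The identification time is collected. Video from injection to the first visualized node is required (7.1.2), and SAP 4.5.1 handles reviewed images that show no visualization. These would help expose a changed call. None of them is a condition for counting: the 0.2 mg rule does not use Likert, the identification time is per participant rather than per node, and the external reading is described only for the signal background ratio.

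Third, a reader might infer that 7.1.1 is what lets the investigator know the gamma result before making the call. It is not. Protocol 1.1, 4.1 and 6.1.1 provide for a repeat near-infrared look after gamma-first detection, so that knowledge is present in the operating room by design. The repeat look is still an actual observation. What post-operative completion mainly adds is knowledge of pathology, and attribution without any look. Pathology shows whether tissue is lymphatic or metastatic, not whether it fluoresced.

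Finally, the VRC Charter, Imaging Charter and eCRF Completion Guideline are not among the documents and may already fix the timing of entry.

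**Conclusion.** The inconsistency is real and worth correcting. As written, an ASP5354 attribution entered after pathology complies with 7.1.1 and counts under SAP 4.4.1. It would also count toward the 3-of-3 rule, where one call can switch the branch.

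The size of any bias cannot be estimated from the documents. The illustration (51% to 55–61% at p = 0.8) rests wholly on an assumed 10% to 25% re-crediting of misses, which nothing in the documents supports or excludes.

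Four stronger conclusions might be inferred, and the documents do not bear them out:

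- **That the main input to dose selection is compromised.** The VRC uses the totality of the data, and no input is ranked above the others.
- **That a failing dose could escape the stop rule.** The rule also stops a dose when all participants score 0 or 1 on Likert, which is fixed during surgery. A later Yes does not undo that.
- **That the first branch settles the outcome.** Both branches include 0.6 mg, and dose levels may later be expanded, closed or added.
- **That the sentinel label must also be fixed before pathology.** No section sets a time for that label, so there is no conflict to resolve.

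**What to change.** In Protocol 7.1.1, state that the participant-level Yes/No and the per-node method of identification reflect the intraoperative near-infrared observation, including the permitted repeat look after gamma detection, and are recorded before any pathology result. Limit the post-operative option to items such as histopathology. This brings 7.1.1 into line with 1.1, 4.1 and Table 1. Carry the same rule into the eCRF Completion Guideline.

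In SAP 4.3.1 and 4.4.1, add that a node or participant counts as identified by ASP5354 only on that intraoperative entry, and that later changes are listed but not counted.

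The cost is a few sentences in 7.1.1, the guideline and the SAP, with no change to surgical procedure or patient care. The one small downside is that a node attributed to ASP5354 only after surgery would be listed and not counted.

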1.2 Study Schema

Figure 1 Study Schema

[figure not shown]
[figure not shown]
[figure not shown]

Figure 2 Dose Cohort Schema (Enrollment for breast cancer and melanoma population will be performed independently and simultaneously)

LN: lymph node; N: number of participants; SLN: sentinel lymph node; VRC: Visualization Review Committee

Footnotes continued on next page

- Enrollment of breast cancer and melanoma participants will be performed independently and simultaneously. Starting dose will be 0.2 mg for the initial 3 participants in each tumor type.
- VRC review will be held when initial 3 participants have completed the surgical procedures at the 0.2 mg dose level to decide whether to enroll participants at the 0.05 mg and 0.6 mg dose levels or the 0.6 mg and 1 mg dose levels. If LN visualization with histopathologic confirmation occurs in the first 3 participants in each indication, then dose level expansion will occur and an additional 3 participants in each indication will be enrolled first with the 0.05 mg dose, followed by another 3 participants with the 0.6 mg dose. If < 3 participants at 0.2 mg dose level have LN visualization with histopathologic confirmation on VRC review, 3 participants will be enrolled sequentially in the 0.6 mg and 1 mg dose levels.
- The second VRC review will be performed for the initial dose levels (0.05, 0.2 and 0.6 mg or 0.2, 0.6 and 1 mg) for breast cancer and melanoma prior to further enrollment of participants. Data for the 9 participants in the first 3 dose levels who completed the SLN biopsy will be assessed to decide whether to: 1) expand a dose under evaluation in 3 participants increments up to 12 participants; 2) stop a dose in which case additional participants would not be added to a dose level; 3) add a new dose level(s); or 4) define a dose as optimal.
- Based on VRC review of the initial 3 doses levels of 3 participants:
 - If 0 doses remain, then a 1 and 2 mg or 2 and 4 mg (breast cancer only) dose will be added
 - If 1 dose remains, then the 1 and/or 2 mg dose will be added.
 - The 4 mg dose level will be added for breast cancer participants if only the 2 mg dose level has visualization.
- Up to 12 participants will be assigned to receive single doses of ASP5354 at each initial dose levels (0.05, 0.2 and 0.6 mg or 0.2, 0.6 and 1 mg) or added dose levels (1, 2 or 4 mg [breast cancer only]) for breast cancer or melanoma.

1.3 Schedule of Assessments

Table 1 Schedule of Assessments

Assessments	Screening Period ^{††}	Treatment Period			Safety Follow-up Period
Day	-28 to -1	1 (Operation)			10 (Outpatient) ¹
Window		Preoperative	Intraoperative	Postoperative	
Visit Number	1		2		3
Informed Consent	X				
Inclusion/Exclusion Criteria	X				
Primary Diagnosis of Target Disease ²	X				
Medical History ³	X				
Demographics ⁴	X				
Drug and Alcohol Screen ⁵	X [†]				
Physical Examination ⁶	X	X		X	X
Vital Signs ⁷	X	X		X ⁸	X
Clinical Laboratory Tests ⁹	X [†]	X		X ⁸	X
Height ⁷	X				
Body Weight ⁷	X				X
Serum or Urine Pregnancy Test ¹⁰	X [†]				X
ECG ¹¹	X	X	X	X	X
Dosing ASP5354 ¹²			X		
Blood Sampling for ASP5354 Pharmacokinetics ¹³		X	X		
Confirmation of Urine or Skin Coloration ¹⁴			→	→	→
Investigator Evaluation for LN Visualization ¹⁵			X		
Record Surgery ¹⁶			X		
Previous/Concomitant Medications	X	X	X	X	X ¹⁷
AE Assessment	X	X	X	X	X ¹⁷
Study Participant Feedback Questionnaire	X				X

Footnotes and abbreviations on next page

AE: adverse event, ECG: electrocardiogram; IP: investigational product; IRT: interactive response technology; LN: lymph node; NIR-F: near-infrared fluorescence; TNM: tumor, nodes and metastases

† These assessments will be performed by a local laboratory and the results of these assessments must be obtained prior to participant enrollment.

†† The assessments scheduled for the screening period can be done on day 1 if all eligibility criteria can be confirmed prior to registration in the IRT and prior to treatment. If screening procedures are performed on day 1, physical examination, vital signs, clinical laboratory tests, ECG, previous/concomitant medications and AE assessment will be done once.

1. If a participant discontinues early from the study, day 10 outpatient visit procedures will be performed upon study discontinuation.
2. Primary diagnosis of the target disease will include:
 - Breast cancer: T categorization in TNM classification, location of tumor (left breast, right breast or other)
 - Melanoma: T categorization in TNM classification and location of tumor (Extremities [upper/lower, left/right], Trunk, Head and Neck, Other), Tumor Thickness and Ulceration status.
3. Medical History includes all significant medical conditions that have occurred or are currently ongoing. The medical condition, onset date, and recovery date will be collected.
4. Demographic information will be collected for all participants at screening and will include age, sex, race, ethnicity, weight and height.
5. Drug screen and alcohol screen will be performed by the study site's preferred method.
6. A full physical examination will be performed at screening (visit 1). Body systems to be evaluated include general appearance, skin, lymphatic, head and neck, ears, nose and throat, chest and lungs, cardiovascular, abdomen, extremities, musculoskeletal and neuromuscular. At visit 2 and follow-up (visit 3), a full physical examination is not mandatory, but a symptom-directed physical examination will be performed.
7. Vital signs include blood pressure, pulse and respiratory rate. All vital signs should be measured within 1 week prior to IP administration at the screening visit. All vital signs will be measured with the participant in the sitting or supine position. Height and weight will be measured using standard institution practice and equipment.
8. Postoperative vital signs and clinical laboratory tests will be collected within 2 hours following the end of surgery.
9. Clinical laboratory tests include blood collection for hematology (complete blood count) and serum chemistry and urine samples for urinalysis. These assessments will be performed by a local laboratory.
10. This assessment will be required only for participants who are women of childbearing potential (see [Section 10.2, Appendix 2 Contraception Requirements]).
11. Standard 12-lead ECGs will be taken per site's standard procedure at screening, preoperative and safety follow-up period. Intraoperative ECG monitoring will occur at 30 minutes postdose (15 min \leq and $<$ 45 min). A 12-lead ECG is not mandatory for intraoperative and postoperative ECG and assessment can be based on the rhythm strip or other site standard ECG as per the site's standard of care routine for cardiac monitoring.
12. ASP5354 will be injected at a minimum of 2 and up to 4 sites of equally divided injections. The exact date and time and location (i.e., 3 and 9 o'clock position of tumor) of IP administration will be documented.
13. Blood samples for pharmacokinetics of IP and possible metabolite(s) (if applicable) will be collected from every participant. A single pharmacokinetic sample will be collected at each of the following time points: prior to dose, approximately 10 minutes, 30 minutes, 60 minutes and 90 minutes postdose, and at the end of surgery.
14. The occurrence of green coloration of the urine or skin will be monitored throughout the study. If observed, any visual green coloration abnormalities will be recorded as an AE. If it occurs for participants who have an urethral catheter in place, the color of urine will be assessed during surgery and every 120 minutes (\pm 30 minutes window) after the end of surgery until it resolves or the participant is discharged, whichever is earlier. If no urethral catheter is in place, voided urine will be assessed for green coloration and the time collected until it resolves or the participant is discharged, whichever is earlier. The start and stop date and time will also be recorded. The occurrence of green coloration of the skin will be recorded as an AE any time after dose administration. The start and stop date and time will be recorded. Skin coloration will be followed up until it resolves or the participant is discharged, whichever is earlier.

Footnotes continued on next page

15. Surgeon evaluation for LN(s) visualization includes incidence of visualization of the LN(s) and distal or second tier LN(s) and the Likert Scale for qualitative response of the intensity of fluorescence. After administration of ASP5354, visualization of the LN(s) will be assessed first using a NIR-F imaging system followed by confirmation with the gamma probe. Once lymphatic mapping is completed, gamma probe will be used per SoC. For all the LNs observed by ASP5354, gamma probe will be attempted to measure radioactivity. If the LN is not observed with NIR-F after approximately 15 minutes following injection for breast cancer participants and approximately 15 to 30 minutes for melanoma participants depending on the location of the tumor and LNs, the investigator can proceed to use the gamma probe for LN detection. When the LN is detected with the gamma probe first, radioactivity will be measured and then NIR-F imaging should be attempted again for LN visualization. During surgery, parameters will be recorded such as time of incision and number of LN(s).
16. Fluorescence images will be captured and recorded during the entire surgery and archived.
17. If a participant experiences an AE or change in concomitant medications during the follow up period, the participant should call the study site to inform any of these changes. Should the participant develop a hypersensitivity reaction, an additional blood sample for determination of histamine and tryptase concentrations should be taken as soon as possible after the onset of the hypersensitivity reaction.

